## 6.11 Main medications that can interact with 5 FU

Metronidazole (Flagyl®) and ornidazole: the concomitant administration of metronidazole can enhance toxicity of 5-FU by decreasing its clearance.

- Allopurinol (Zyloric®): concomitant administration of this product must be avoided (loss of 5-FU efficacy).

-Phenytoin : Risk of convulsions due to decreased digestive absorption of phenytoin alone by the cytostatic, or risk of increased toxicity or loss of cytotoxic efficacy due to increased hepatic metabolism by phenytoin or fosphenytoin.

-Antivitamin K : Significant increase in the effect of antivitamin K and hemorrhagic risk. If association cannot be avoided, more frequent monitoring of INR. Dosage adjustment of antivitamin K during cytotoxic treatment and 8 days after discontinuation.

-Interferon alpha : Increased gastrointestinal toxicity of 5-FU.

-Drugs that may affect dihydropyrimidine dehydrogenase (DPD) activity :

A clinically significant interaction between the antiviral Sorivudine and fluorouracil prodrugs has been observed, resulting from the inhibition of dihydropyrimidine dehydrogenase, the enzyme responsible for the catabolism of fluorouracil and its prodrugs, by Sorivudine or chemically related analogues. Precautions should be taken when using fluorouracil in combination with drugs that may affect the activity of dihydropyrimidine dehydrogenase.

-Cimetidine may increase the blood concentration of fluorouracil.

In the majority of cases, cytostatics are given in combination, which leads to an increase in efficacy, but at the cost of a possible increase in toxicity.

-Yellow fever vaccine is absolutely contraindicated

Risk of fatal generalized vaccine disease.

-Live attenuated vaccines (except antiamarile) is not recommended

Risk of life-threatening, widespread vaccine-preventable disease. This risk is increased in subjects already immunocompromised by the underlying disease. Use inactivated vaccine when available (polio).

## 6.12 Main medications that can interact with Oxaliplatin

The drugs that prolong QTc and/or cause twisting spikes have to be used with caution (see appendix 8).

## 7. Blinded independent central review (BICR)

A central review of CT-scans is planned for patients found progression-free at 48 weeks. They will be submitted to a independent panel of radiologists for review of tumor response.

### 7.1. Shipment procedure and storage

Compact Discs (CDs) will be anonymized and sent by postmail or transferred to PACS server of ICM if it's possible technically.

It is important to the integrity of the study that all imaging studies are forwarded to the independent panel of radiologist in a timely manner throughout the study (by the end of treatment of patient).

## 8. Ancillary Studies

### 8.1. Activity of DDR1 as a predictor of efficacy of regorafenib

Paraffin-embedded human solid tissue blocks will be sent off at room temperature at the end of the inclusions and addressed to:

[name] [name] collection manager Institut régional du cancer de Montpellier Centre de ressources biologiques [name] [contact] – [contact] [contact]

----------------------------------------------------------------------------------------------------------------------------------------------------------------------------------------------------------------------------------------------------------------------------------------------------------------------------------------------------------------------------------------------------------

Paraffin-embedded human solid tissue blocks will be returned to the home institution upon completion of ancillary study.

**Actually, with this translational research, we aim to assess DDR1 activity as a predictor of efficacy in mCRC patients treated with a regorafenib-based therapy.**

**The research will be led by [name], Centre de Recherche en Biologie cellulaire de Montpellier**

**Methodology:** *DDR1 activity in CRC samples:* DDR1 activity will be measured from tumor protein-lysates with the pathscan phospho-DDR1 (panTyr) ELISA kit (CST Company).

*Inhibition of DDR1 metastatic activity by regorafenib:* DDR1 kinase overexpression in HCT116 and SW620 CRC cells increases their invasive capacities in Boyden chambers and their capacity to form colosphere when cultured in suspension in the presence of collagen (17). We will test the capacity of regorafenib (1-500nM) to block these DDR1 transforming properties *in vitro*. DDR1 kinase overexpression in Luc+ SW620 cells increases their metastatic abilities when spleen-injected in nude mice (17). We will test the capacity of regorafenib (50mg/kg/d) to block this DDR1 metastatic function. Drug treatment will be started when metastatic nodules are already developed in recipient animals (i.e. at day 7). Metastatic development will be analyzed by measuring over time luciferase activity in live animals (imaging of the whole animal) and a metastatic index will be deduced from livers of sacrificed animals.

## 8.2. cfDNA monitoring

[figure not shown]
### 8.2.1. Sample timeline

Three EDTA tubes will be collected at baseline, every 8 weeks during treatment and at the end of treatment (not supplied).

### 8.2.2. Processing of samples

Three 7-ml EDTA tubes will be taken at various times and centrifuged within 4 hours at 1200g for 10 minutes at 4°C. After centrifugation, the plasma will be frozen at -80°C until shipment.

**[name]**  
**Equipe de recherche intégrée en Cancérologie de**  
**Montpellier (INSERM)**  
 Institut de Recherche du Cancer de Montpellier (IRCM)  
 [name]  
 [name]  
 Tél : [name] ; [name]  
 [contact]  
[[contact]](mailto:[contact])

cfDNA will be extracted using either the QIAmp DNA blood Mini kit (Qiagen, CA) or the Maxwell automatic extractor according to the standardized guidelines which were defined for pre-analytical conditions (unpublished data).

CfDNA total concentrations and fragmentation level will be determined by either by targeted or sequencing methods.

A banking sample is planned at ICM-CRB, Montpellier.

## 9. Subject withdrawal/end of study

### 9.1. DISCONTINUATION OF TREATMENT

Discontinuation of treatment does not represent withdrawal from the trial. As certain data on clinical events beyond treatment discontinuation are important to the study, they must be collected through the subject's last scheduled follow-up, even if the subject has discontinued treatment. Therefore, all subjects who discontinue trial treatment prior to completion of the treatment regimen will still continue to participate in the trial.

Patient may be discontinued from study treatment at any time if the patient, the Investigator, or the Sponsor feels that it is not in the patient's best interest to continue on study. The following is a list of possible reasons for early discontinuation of study treatment:

- Disease progression (unless there is reasonable evidence of clinical benefit to justify continuation on treatment – to be discussed with the Sponsor)
- In the investigator's opinion, continuation in the study treatment would be detrimental to the patient's well-being
- Protocol violation requiring discontinuation of study treatment
- Patient is not compliant with study procedures
- Patients with a β-HCG test consistent with pregnancy. Pregnancy will be notified to the sponsor.
- Any adverse event that cannot be adequately managed with dose modifications, including dose interruption > 28 days (unless there is reasonable evidence of clinical benefit to justify continuation on the protocol – to be discussed with the Sponsor)
- Discontinuation of treatment during more than 4 weeks
- Patient death
- New cancer
- Lost to follow-up

(The Investigators should make every effort to recontact the patient to identify the reason why he/she failed to attend the visit, and to determine the patient health status, including at least the vital status. Attempts to contact such patients must be documented in the patient's records (e.g., times and dates of attempted telephone contact, receipt for sending a registered letter).

## 9.2. WITHDRAWAL FROM THE TRIAL

A subject must be withdrawn from the trial if the subject or subject's legally acceptable representative withdraws consent from the trial.

If a subject withdraws from the trial, they will no longer receive treatment or be followed at scheduled protocol visits.

## 9.3. END OF STUDY

The end of the trial corresponds to the last follow-up of the last patient.

## 9.4. ASSESSMENT CRITERIA

Phase I: Identify the maximum-tolerated dose (MTD) of Folfirinox combination with regorafenib in Patients with metastatic colorectal cancer.

Phase II:

Non-progression rate (OR+SD): The tumor response will be assessed by the investigator using RECIST guidelines v1.1 (2009). The non-progression rate will be presented as a percentage with a 95% confidence interval.

Objective response (OR): The tumor response will be assessed by the investigator using RECIST v1.1 criteria, from the first course of chemotherapy, until disease progression. Patients with suggestive symptoms of disease progression should be evaluated at the time of onset of symptoms. An objective response is defined as a complete (CR) or a partial (PR) response.

The best objective response rate will be reviewed at the end of treatment and presented as a percentage with a confidence interval of 95%.

Survival:

Progression-free survival (PFS): Survival Delays will be calculated in months from the date of inclusion to the date of the considered event: First documented disease progression or death from any cause.

Living patients without disease progression will be censored at the last known date.

Rates and median PFS will be estimated using Kaplan-Meier method and presented with its 95% confidence interval.

Overall survival (OS): The overall survival time will be calculated in months from the date of inclusion to the date of death from any cause. Living patients will be censored at the last known date.

Rates and median overall survival will be estimated using the Kaplan-Meier product limit method and presented with its 95% confidence interval.

The median follow-up will be calculated using the "reverse Kaplan-Meier method".

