STUDY ENDPOINTS	
2. Non-Hematologic DLT:
 
 
➤ Grade <math>\geq 3</math> (CTCAE v5) non-hematologic toxicity, except:           
 
-Grade 3 nausea, vomiting, diarrhea, and Grade 2 alopecia
 
-any untreated HFSR that can be adequately controlled with medical intervention,
 
-Grade <math>\geq 3</math> lipase elevation without signs of pancreatitis,
 
 
 
➤ Grade <math>\geq 2</math> posterior reversible encephalopathy syndrome (PRES),
 
➤ Grade <math>\geq 2</math> retinopathy,
 
➤ Liver-specific DLTs are:           
 
-Drug-related gr. 3-4 bilirubin increase
 
-Drug-related gr. 3-4 AST and/or ALT increase
 
-Drug-related AST and/or ALT increase <math>> 3 \times</math> ULN and associated with concurrent bilirubin increase(<math>> 2 \times</math> ULN)
 
 
 
 
3. Hematologic DLT:
 
 
➤ Grade 4 (NCI-CTCAE v5) neutropenia lasting <math>> 3</math> days,
 
➤ Grade 3 Febrile neutropenia (ANC <math>< 1,000/\text{mm}^3</math> with fever <math>\geq 38.5^\circ\text{C}</math>) (NCI-CTCAE v5),
 
➤ Grade 4 Febrile neutropenia (life-threatening consequences; urgent intervention indicated),
 
➤ Grade 4 (NCI-CTCAE v5) anemia (i.e. life threatening consequences; urgent intervention indicated),
 
➤ Platelets <math>< 25,000/\text{mm}^3</math> or platelets <math>< 50,000/\text{mm}^3</math> associated with bleeding,
 
➤ INR or PTT elevation of Grade <math>\geq 3</math> (NCI-CTCAE v5) with associated bleeding,
 
➤ Grade <math>\geq 3</math> hemorrhage/bleeding events (NCI-CTCAE v5).
 
 
Phase II: 48-week disease-control rate (defined as the rate of non-progressing patients after central review, at 48-week post-initiation of therapy, to all treated patients).
 
Secondary endpoints:
 
Phase II :
 
Progression-free survival (PFS), defined as the time from date of inclusion to date of first observed disease progression (investigator's radiological or clinical assessment) or death due to any cause, if death occurs before progression is documented. A central review of CT-scans is planned for patients found progression-free at 48 weeks. Patients without tumor progression or death at the time of analysis will be censored at their last date of tumor assessment,

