**Prophylactic G-CSF will be systematically given after each course from Day-7 to Day 12.**

**REGORAFENIB** will be given orally at a dose of 80 to 160 mg, as per dose-level, once daily on days 4 to 10 of each cycle

Tumor assessments (computed tomography (CT) or magnetic resonance imaging (MRI)) of the chest, abdomen, pelvis (if patient allergic to iodine contrast agents) will be performed at the baseline, every 8 weeks thereafter.

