#### **Follow-up every three months for 3 years**

- Vital status
- Anti-cancer medications
- Physical examination
- Adverse events documentation (only for unstabilized adverse events since the end of treatment)

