#### Phase II

With a one-stage Fleming design,  $\alpha = 5\%$ ,  $\beta = 20\%$ ,  $p_0$  (the probability of inefficiency maximum) = 35% and  $p_1$  (the probability of minimum efficiency) = 50%, it would be necessary to include 65 evaluable patients (69 patients/ 5% non-evaluable patients).

The association can be considered sufficiently effective (reject null hypothesis) if there are at least 29 success (48 weeks disease control rate) out of 65 evaluable patients, the success rate is significantly greater than 35%.

The association can be considered insufficiently effective (reject alternative hypothesis) if there are 28 or less success out of 65 evaluable patients, the success rate is significantly lower than 50%.

In total, a maximum of 87 (=18 patients for phase I + 69 patients for phase II including 6 patients treated at the RP2D during the phase I) patients will be included.

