### 10.3. STATISTICAL METHODS

A statistical analysis plan (PAS) will be written before the closed database. All statistical analyses will be performed on ITT population, on PP population for efficacy analysis and on Safety population for safety analysis. Populations are defined in section 10.2.

Descriptive analyses will be performed using median and range for continuous parameters, frequency and percentage for categorical variables.

Incidence rate of DLT and Incidence rates of adverse events and serious adverse events will be carried using frequencies and percentages at each dose level for phase 1.

The primary phase II endpoints 48 weeks disease control rates, will be described using percentage and its associated 95% confidence interval.

The median follow-up will be calculated using the reverse Kaplan-Meier method with its confidence interval of 95%.

All event free survival (PFS, OS) will be estimated using the Kaplan-Meier method, and then described using medians and rates with their associated 95% confidence interval.

Statistical analyses will be performed with STATA software (Stata Corporation, College Station, TX, USA).

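### PFS is censored at the last tumour assessment in the synopsis and section 2.2.2, but at the last known date in section 9.4, which counts unscanned follow-up as progression-free

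*Combined protocol and SAP*

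**What the plan says.** The synopsis (secondary endpoints) and section 2.2.2 give one PFS rule: "Patients without tumor progression or death at the time of analysis will be censored at their last date of tumor assessment". Section 2.2.2 uses the same rule for time to recurrence under maintenance.

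Section 9.4 gives another: "Living patients without disease progression will be censored at the last known date". It does not define that date. Its overall survival rule is "Living patients will be censored at the last known date", so last contact is the natural reading for PFS too.

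Section 10.3 says only that "All event free survival (PFS, OS) will be estimated using the Kaplan-Meier method". It gives no censoring rule and leaves the SAP to be written before the database is closed.

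Three other places determine whether the dates differ in practice:

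- Section 9.1: "all subjects who discontinue trial treatment prior to completion of the treatment regimen will still continue to participate in the trial".
- Section 5.5, under "Follow-up every three months for 3 years", lists vital status, anti-cancer medications, physical examination and unresolved adverse events. It lists no imaging.
- The synopsis says that tumour imaging "will be performed at the baseline, every 8 weeks thereafter", with no stated stop. Section 5.3 places the 8-weekly evaluation within the treatment period.

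**The concern.** The same data can yield two PFS curves, and the plan does not say which will be reported. Under section 9.4, a patient who stops treatment without progression and is later only known to be alive stays at risk, and counts as progression-free, over months without a scan. If some progression in those months goes unrecorded, the curve is biased upward.

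Section 6.4 makes such patients possible. After 12 cycles only patients who are unprogressed and still unresectable continue regorafenib, and they do so until progression or toxicity. Resected patients and those who stop for toxicity can therefore leave treatment unprogressed.

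PFS is not tested. However, section 1 names a 9.4-month median as the benchmark, so readers will compare the reported median with it. Section 2.1.2 also correlates PFS with DDR1 activity and RAS-mutant cfDNA. While both rules stand, the choice could be made after the data are seen.

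**Working it through.** **Plan's own figure.** The plan gives no sample size or power for PFS. The primary-endpoint size reproduces: [(1.645·√(0.35·0.65) + 0.842·√(0.5·0.5)) / 0.15]² = 64.6, rounded up to 65; 65/0.95 = 68.4, rounded up to 69. Only the 69 patients and the 5% allowance are used below.

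**Direction.** Kaplan-Meier multiplies factors 1 − d/n over event times. If both rules count the same events, each d is the same. The last contact is never earlier than the last scan, so each n under section 9.4 is equal or larger. Every factor, and so the whole curve, is equal or higher. In 24,000 simulated trials the 18-month estimate under section 9.4 was never below the one under section 2.2.2.

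**Size: inputs.**
- From the documents: median PFS 9.4 months (section 1); n = 69 (section 10.1); follow-up uniform over 15–27 months (12-month phase II inclusion ending March 2021, study end June 2022).
- Assumed: exponential PFS; death a mean of 16 months after progression (from the section 1 medians, 25.6 − 9.4 = 16.2); a fraction f stops imaging at a uniform 2–8 months.
- Share actually leaving unprogressed: f times the mean of exp(−0.0737u) over u = 2 to 8, where 0.0737 = ln 2/9.4. That mean is 0.70, so f = 0.07, 0.20 and 0.40 give 5%, 14% and 28%.

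**Size: result.** Mean Kaplan-Meier median in months, section 2.2.2 rule vs section 9.4 rule, 6,000 trials per cell. Columns give the share of later progressions recorded clinically.

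| Off imaging | 0% recorded | 50% recorded | 100% recorded |
|---|---|---|---|
| 5% | 9.56 vs 9.82 (+0.26) | 9.49 vs 9.66 (+0.17) | 9.40 vs 9.48 (+0.08) |
| 14% | 9.70 vs 10.61 (+0.91) | 9.44 vs 10.05 (+0.61) | 9.15 vs 9.46 (+0.31) |
| 28% | 9.93 vs 12.20 (+2.27) | 9.32 vs 10.62 (+1.30) | 8.86 vs 9.49 (+0.63) |

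With nobody off imaging, both rules give 9.50.

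**If off-treatment patients are scanned.**
- One 48-week scan, no clinical recording: medians 9.74 vs 9.74, 10.18 vs 10.21 and 10.72 vs 10.80. The gap moves later: 18-month PFS 25.8% vs 27.5%, 25.7% vs 29.4% and 25.4% vs 32.1%.
- Scans every 8 weeks until progression: medians 9.5 vs 9.5; 18-month PFS 25.9% vs 26.5%.

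**Second model.** Here progression is dated on the 8-week scan grid, scans stop at a uniform 8–48 weeks, the median from progression to death is 14 months, and nothing is recorded clinically (1,500 trials per cell). With a true median of 9.4 months and 10%, 20%, 30% or 40% of patients assigned to stop scans, 48-week PFS is 44.6% vs 46.3%, 44.8% vs 48.2%, 45.1% vs 50.2% and 45.6% vs 52.3%. The rises are 1.7, 3.4, 5.1 and 6.7 points. Medians move unevenly on the grid: 11.0 months under both rules at 10% and 20%, then 11.0 vs 11.7 and 11.0 vs 12.9.

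**The case against.** The contradiction itself is not in dispute. The objections concern its size and the remedy.

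- **Scanning may continue.** Section 9.4 says response is assessed until progression, the synopsis sets no end to the 8-weekly scans, and the primary endpoint needs status at 48 weeks. If scans do continue, the rules nearly coincide. This stands as a real possibility, but the first statement sits under objective response and the follow-up list contains no imaging.
- **The time is not wholly unassessed.** Clinical progression is an event, follow-up includes a physical examination, and section 9.4 asks for evaluation when symptoms arise. This stands, and is why the results run from 0% to 100% clinical recording.
- **Last-assessment censoring is not unbiased.** This stands. With every later progression recorded, section 9.4 stays near 9.5 months while section 2.2.2 reads low (8.86 at 28% off imaging). There the gap is error in the recommended rule. With none recorded, section 2.2.2 itself reads slightly high (9.93), because unscanned time before a death still counts.
- **The inputs are assumed.** The 14% and 28% shares have no source, and the 5% is borrowed from the non-evaluable allowance. At 5% the shift is small beside a sampling standard deviation of about 1.7 months for the median, and with progression dated on the scan grid the two medians were identical in about 76–91% of trials. This stands.
- **Events might differ.** Section 9.4 refers to documented progression, section 2.2.2 to observed radiological or clinical progression. If these were applied differently, the ordering of the curves would no longer be guaranteed.

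**Conclusion.** The concern holds. Two incompatible PFS censoring rules stand in current text, and the one in section 9.4 credits unscanned follow-up as progression-free. For the same events, its curve is never the lower of the two, and it is biased upward whenever progression after imaging stops goes unrecorded.

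The effect on the median runs from nil, if scans continue until progression, through 0.1–0.3 months at 5% off imaging, to 0.6–2.3 months at 28%. These figures rest on the assumed off-imaging shares and survival model and should not be read as forecasts. The contradiction is certain; the size is not. The case for last-assessment censoring is that the endpoint definition already states it and that it does not presume unscanned patients to be progression-free. It is not that the rule is unbiased in every scenario.

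The consequence is limited to a descriptive secondary endpoint and the translational correlations that use it. The primary decision rule of 29 successes out of 65 does not use PFS censoring. The correction should be made, but the trial's main conclusion does not depend on it.

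**What to change.** In the PFS paragraph of section 9.4, replace the censoring date with the date of the last tumour assessment, matching the synopsis and section 2.2.2. Keep the last known date for overall survival only. Carry the same rule into the SAP.

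The cost is one sentence, with no change to sample size, visits or patient burden. Reported PFS may be slightly less favourable, and the rule keeps the imperfections described above.

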## 10. Statistical considerations

### 10.1. SAMPLE SIZE

#### Phase I

A standard 3 + 3 design will be followed in the dose escalation. A maximum of 24 patients will be enrolled in phase I.

